### 2.2.1 Exploratory Endpoints

The exploratory endpoints for this study include the following:

- Safety and tolerability endpoints:
  - Columbia–Suicide Severity Rating Scale (C–SSRS)
  - Extrapyramidal Symptom Rating Scale–Abbreviated (ESRS-A) score
  - Sexual dysfunction defined as a CSFQ-14 total score of  $\leq 47$  for men and  $\leq 41$  for women
  - Vital signs
  - Body weight
  - Potentially clinically important laboratory values
- Efficacy endpoints:
  - Change from Baseline in Hamilton Depression Scale (17 items) (HAMD-17) total score
  - Treatment responder rates. Treatment response is defined as a reduction from Baseline in HAMD-17 total score of 50% or more.
  - Treatment remission rates. Treatment remission is defined as a HAMD-17 total score  $\leq 7$ .

- Change from Baseline in Clinical Global Impression–Severity (CGI-S) score for depressive symptoms
- Change from Baseline in Sheehan Disability Scale (SDS) score
- Change from Baseline in the Changes in Sexual Functioning Questionnaire Short Form (CSFQ-14) score
- Change from Baseline in Karolinska Sleepiness Scale (KSS) score

### **3 STUDY DESCRIPTION**

#### **3.1 Overview of Study Design**

This study will be a 52-week open-label extension study to evaluate the long-term safety and tolerability of pimavanserin in subjects with major depressive disorder and inadequate response to antidepressant treatment. Up to approximately 80 sites will participate in this study. The total duration of exposure to pimavanserin may be greater than 52 weeks (e.g., up to 58 weeks) as subjects may have been treated with pimavanserin in the antecedent studies, ACP-103-054 and ACP-103-059. The duration of participation for individual study subjects will be up to approximately 56 weeks.

The study will have two periods ([Figure S-1](#)):

- Open-label treatment period (52 weeks)
- Safety follow-up period (at least 30 days)

The end of treatment (EOT) visit for the antecedent study, Study ACP-103-054 or Study ACP-103-059, is the Baseline visit for the present study.

Subject consent for the present study must be obtained prior to the final procedures being performed at the antecedent study's (ACP-103-054 or ACP-103-059) end of treatment (EOT) visit. Data from the EOT procedures of Studies ACP-103-054 and ACP-103-059 will be carried over to the ACP-103-055 study to be included as baseline information for the present study and this visit will be considered Baseline (Visit 1).

The study completion date (or when a subject is considered to have completed the study) is defined as the date the final subject, across all sites, completes their final protocol-defined assessment. Please note that this includes the safety follow-up visit/contact, whichever is later. Procedures for when a subject is lost to follow-up are provided in [Section 4.5](#).

##### **3.1.1 Open-label Treatment Period (52 Weeks)**

Eligible subjects will begin pimavanserin once-daily dosing at 34 mg. Subject eligibility will be assessed by the site and the Sponsor through an eligibility review process.

During the treatment period, clinic visits will be conducted at Baseline and Weeks 2, 4, 8, 12, 16, 28, 40, and 52 (EOT), or upon early termination (ET) from the study.

Study drug will be dispensed to the subject to take home at the Baseline visit. The subject will be instructed to take the first dose of study drug on the day after the Baseline visit.

All concomitant permitted medications should remain stable during the study, including the background antidepressant.

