**Table S-1 Schedule of Events and Assessments for ACP-103-055**

Period	Baseline c	Treatment Period								Safety Follow-Up m	
	Visit Number	1	2	3	4	5	6	7	8		(EOT/ET) 9
Visit Week a	Week 0	Week 2	Week 4	Week 8	Week 12	Week 16	Week 28	Week 40	Week 52	Unscheduled Visit l	Week 56
Type of visit b	Clinic	Clinic	Clinic	Clinic	Clinic	Clinic	Clinic	Clinic	Clinic	Clinic	Phone call
Visit window (# days)		±3	±3	±3	±3	±7	±7	±7	+7		+7
Informed consent and if applicable, privacy forms c	X										
Inclusion/exclusion criteria	X										
Medical history, medication history, and demographics d	X										
Psychiatric history d	X										
Physical examination	X						X		X		
Vital signs and weight	X	X	X	X	X	X	X	X	X	X	
ECG e	X	X	X	X	X	X	X	X	X		
Clinical laboratory tests f	X				X				X		
Pregnancy test g	X		X	X	X	X	X	X	X		
Urine drug screen	X				X				X		
ESRS-A	X	X	X	X	X	X	X	X	X	X	
C-SSRS	X	X	X	X	X	X	X	X	X	X	
HAMD-17 h	X	X	X	X	X	X	X	X	X		
CGI-S	X	X	X	X	X	X	X	X	X		
SDS	X		X		X		X		X		
CSFQ-14	X	X	X	X	X	X	X	X	X		
KSS	X	X	X	X	X	X	X	X	X		
Concomitant medications	X	X	X	X	X	X	X	X	X	X	X
Assessment of AEs i	X	X	X	X	X	X	X	X	X	X	X
Dispense study drug	X j,k		X	X	X	X	X	X	X	X m	
Study drug accountability	X k	X	X	X	X	X	X	X	X	X	
Review of background antidepressant adherence	X	X	X	X	X	X	X	X	X	X	X

Table footnotes and abbreviations on next page.

Abbreviations: AE=adverse event; CGI-S=Clinical Global Impression–Severity; COVID-19=coronavirus disease 2019; CSFQ-14=Changes in Sexual Functioning Questionnaire Short Form; C-SSRS=Columbia–Suicide Severity Rating Scale; ECG=electrocardiogram; EOT=end of treatment; ESRS-A=Extrapyramidal Symptom Rating Scale–Abbreviated; ET=early termination; HAMD-17=Hamilton Depression Scale (17 items); KSS=Karolinska Sleepiness Scale; SDS=Sheehan Disability Scale

- a Study visits are designated by weeks and have a  $\pm 3$ -day window (Visits 2 through 5), or a  $\pm 7$ -day window (Visits 6 through 8), or a +7-day window (Visits 9 and 10), and are calculated from the Baseline Visit.
- b If visit is performed remotely due to the COVID-19 pandemic, please refer to [Sections 3.1.3](#) (impact of COVID-19 pandemic), [6.2.6](#) (exploratory efficacy assessments), [6.3.8](#) (safety assessments) and [6.5.1](#) (unscheduled visits) for further information.

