5.3 Analysis Visit Windows

In general, the open-label Baseline assessment will be defined as the last non-missing assessment, including those from repeated and unscheduled measurements, before or on the first open-label dose date. Exceptions to this definition will be handled on a case by case basis.

Efficacy and safety assessments will be summarized by analysis visit as presented in Table 1 below.

Table 1 Analysis Visit Windows

Open-label (OL) Analysis Visit Name	Target Study Day¹	Study Day Interval
OL Baseline	1	≤1 (based on the first OL dose date)
OL Week 2	15	2 to 21
OL Week 4	29	22 to 42
OL Week 8	57	43 to 70
OL Week 12	85	71 to 98
OL Week 16	113	99 to 154
OL Week 28	197	155 to 238
OL Week 40	281	239 to 322
OL Week 52	365	323 to 379
OL Follow-up	395	380 – maximum

¹ If the assessment date ≥ first OL dose date, study day = assessment date - first OL dose date + 1, otherwise study day = assessment date – first OL dose. Study day 1 is the first OL dose date.

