5.3.2 Multiple Measurements within Visit Windows

If more than one assessment falls within a given window then the assessment closest to the target study day will be selected for the by-visit summaries. If two assessments are equidistant from the target day then the chronologically last assessment will be used for summary. Exceptions may be made for incomplete assessments, in which case, more complete assessments may be given priority. Details are provided in a separate programming conventions document.

For safety summaries where the most extreme values should be selected, e.g. overall post-baseline minimum, overall post-baseline maximum, and potentially clinically important values for overall post-Baseline summaries, all non-missing post-Baseline values should be considered, regardless of whether the value is selected for the by-visit summaries. All results will be presented in data listings.

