10.1 Exposure to Study Drug

10.1.1 Exposure to Open-label Pimavanserin

For each subject, the duration of exposure to open-label pimavanserin (open-label last dose date – open-label first dose date + 1) will be calculated and summarized. The number and percentage of subjects within each of the following exposure levels in terms of duration of exposure will also be tabulated: <2 week (1 to 13 days), 2 to <4 weeks (14 to 27 days), 4 to <8 weeks (28 to 55 days), 8 to <12 weeks (56 to 83 days), 12 to <16 weeks (84 to 111 days), 16 to <28 weeks (112 to 195 days), 28 to <40 weeks (196 to 279 days), 40 to <52 weeks (280 to 363 days), ≥52 weeks (≥364 days).

In addition, the maximum dose in the open-label period, final dose in open-label period, and the mean daily dose during open-label period will be determined for each subject and summarized. The mean daily dose will be calculated as the number of pimavanserin tablets taken in the open label period multiplied by 17 (mg) divided by the duration of total exposure in the open-label period in days.

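### SAP Table 1 sets each on-treatment target one day after the scheduled visit, because open-label dosing starts the day after Baseline

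*Protocol*

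**What the plan says.** Three rules meet here.

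- **Visit schedule.** Protocol Table S-1, footnote a, gives Visits 2 to 5 a window of ±3 days, Visits 6 to 8 ±7 days, and the last two "or a +7-day window (Visits 9 and 10), and are calculated from the Baseline Visit". SAP Appendix A repeats this.
- **Start of dosing.** Protocol 3.1.1 states: "The subject will be instructed to take the first dose of study drug on the day after the Baseline visit". Protocol 5.1.3 and SAP 3.1 give the same instruction.
- **Study day.** The footnote to SAP Table 1 states: "If the assessment date ≥ first OL dose date, study day = assessment date - first OL dose date + 1". It adds: "Study day 1 is the first OL dose date".

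Table 1 then gives each analysis visit a target day and an interval; the Week 2 row reads "OL Week 2 15 2 to 21". The target has one use. When a window holds several assessments, SAP 5.3.2 says "the assessment closest to the target study day will be selected for the by-visit summaries", and a tie goes to the later one. SAP 5.3.1 lets unscheduled, early termination and remote assessments compete with the scheduled one.

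**The concern.** Visits are counted from the Baseline visit, study days from the first dose, and the two dates differ by one day. The Table 1 targets fit the visit schedule only if both dates are the same, and SAP 3.1 says they are not.

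The target decides which of two values enters a by-visit table. If it sits a day after the scheduled visit, the rule favours a later, unplanned assessment over a scheduled one taken exactly on time. At stake is which measurement represents a timepoint in the by-visit summaries.

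**Working it through.** **Inputs.** Let B be the Baseline visit date. The week w visit is due on B + 7w (Protocol Table S-1). The first open-label dose is on B + 1 (Protocol 3.1.1, SAP 3.1). Study day = date − first dose date + 1 (SAP 5.3).

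**Step 1: reproduce Table 1.** If dosing began on B, the study day would be (B + 7w) − B + 1 = 7w + 1. For weeks 2, 4, 8, 12, 16, 28, 40 and 52 this gives 15, 29, 57, 85, 113, 197, 281 and 365, which matches all eight targets.

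**Step 2: apply the stated dosing rule.** With the first dose on B + 1, the study day is (B + 7w) − (B + 1) + 1 = 7w. None of the eight targets matches.

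| Week | On-schedule day | Table 1 target | Protocol window in study days | Table 1 interval |
|---|---|---|---|---|
| 2 | 14 | 15 | 11–17 | 2–21 |
| 4 | 28 | 29 | 25–31 | 22–42 |
| 8 | 56 | 57 | 53–59 | 43–70 |
| 12 | 84 | 85 | 81–87 | 71–98 |
| 16 | 112 | 113 | 105–119 | 99–154 |
| 28 | 196 | 197 | 189–203 | 155–238 |
| 40 | 280 | 281 | 273–287 | 239–322 |
| 52 | 364 | 365 | 364–371 | 323–379 |

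Every protocol window lies inside its interval, so no in-window visit goes to the wrong timepoint.

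**Step 3: effect on selection.** Take two assessments on days a < b in one window with target T. The later one is used when a + b ≤ 2T, ties included. For Week 2 the limit is 30 with T = 15 and 28 with T = 14. Only pairs that sum to 29 or 30 change: 13 of the 190 possible pairs (20 × 19 / 2) in days 2 to 21.

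| Scheduled visit made | Later assessment displaces it, Table 1 target | Same, target 7w |
|---|---|---|
| On time | 1 to 2 days after | never |
| 1 day early | 1 to 4 days after | 1 to 2 days after |
| 2 days early | 1 to 6 days after | 1 to 4 days after |
| 3 days early | 1 to 8 days after | 1 to 6 days after |
| Late | never | never |

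**Step 4: the opposite direction.** Suppose a scheduled visit is k days late and an unscheduled assessment was made q days before it. The earlier one is used when a + b > 2T. This means q < 2k − 2 with the Table 1 target and q < 2k with target 7w. For k = 1 the span goes from none to 1 day; for k = 2 from 1 to 3 days; for k = 7 from 11 to 13 days. Moving the target therefore has a small cost for late visits.

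**Step 5: exposure, which does not use Table 1.** SAP 10.1.1 takes last dose − first dose + 1. For a Week 52 visit exactly on B + 364, a last dose that day gives (B + 364) − (B + 1) + 1 = 364 days, in the top row. A last dose the day before gives 363 days, in the row "40 to <52 weeks (280 to 363 days". If the visit is 1 to 7 days later, either timing gives at least 364.

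**The case against.** The strongest reply is that 7w + 1 is a coherent convention: day 15 is exactly 14 days after the first dose, and no section requires an analysis target to equal the nominal visit day. The interval limits do not settle it. The upper limits 21, 42, 70, 98, 154, 238 and 322 are midpoints of the 7w days, while the lower limits 22, 43, 71, 99, 155, 239 and 323 are midpoints of the printed targets. This stands as far as it goes. But visits are not scheduled from the first dose, and the target has a working role, so the symmetric windows of Visits 2 to 8 sit off-centre.

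It is also fair that most displacement of early visits comes from the selection rule and would remain after the fix, as Step 3 shows.

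Two stronger readings are tempting and not supported:

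- **Bias toward normal.** A reader might infer that confirmatory repeats pull by-visit ECG or laboratory tables toward normal. The documents do not say how often or why repeats are made. Table S-1 marks no ECG or laboratory test at unscheduled visits. Vital signs, weight, ESRS-A and C-SSRS are expected there, and anything further is discretionary. A same-day repeat has the same study day and is unaffected. No size can be put on such a drift.
- **A wrong OL Baseline.** A reader might object that Table 1 puts Baseline at day 1 when the visit is study day −1. Baseline is the latest available value up to and including the first dose date, so that target plays no part.

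**Conclusion.** The mismatch is certain from the documents: all eight on-treatment targets are one day later than the visits they represent. The consequence is small. It arises only when a window holds a second assessment at the spacings in Step 3, and only in by-visit summaries. SAP 5.3.2 draws overall post-Baseline extremes from all values, TEAEs are defined by dose dates, and the study is descriptive with no hypothesis tests.

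This assumes that subjects follow the dosing instruction. For anyone who takes the first dose on the visit day itself, an exception SAP 10.1.2 seems to allow for, the printed targets are right. For anyone who starts later than the next day, the gap is wider.

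A reader might also infer that the exposure table wrongly drops completers from the 52-week row. The documents do not support calling that an error. It needs a Week 52 visit exactly on its due day and a last dose the day before, and they do not say whether a dose is taken on that day. It is a separate point, which correcting Table 1 would not change.

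**What to change.** In SAP Table 1, set the on-treatment targets to study days 14, 28, 56, 84, 112, 196, 280 and 364, and keep the existing intervals. This changes one column of the SAP and the matching program input; it needs no new data and no change to study conduct.

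The downside is the one in Step 4: a late scheduled visit can more often lose to an unscheduled assessment shortly before it. This matters most at Week 52, whose window runs from 0 to +7 days, so that in-window visits are on time or late and never early. The SAP should state that this was considered.

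Optionally, show the number of subjects who completed Week 52 beside the ≥52-week row (≥364 days) of SAP 10.1.1, so that a completer with 363 days is not read as an early stop.

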### **3.1.2 Safety Follow-up Period (30 Days)**

A safety follow-up telephone call to the subject will be conducted at least 30 days after the last dose of study drug.

### **3.1.3 Impact of COVID-19 Pandemic**

The emergence of the coronavirus disease 2019 (COVID-19) pandemic has resulted in the implementation of measures designed to ensure subject safety.

Subjects remaining in this study who cannot attend clinic visits are allowed to participate in remote visits via telephone or video, or site staff can conduct the visit in a subject's home. Sites are required to document details of all visits that are administered remotely.

Further details about accommodations and modifications to assessments, relating to the COVID-19 pandemic, can be found in [Sections 5.1.1](#) (home delivery of study drug), [6.2.6](#) (exploratory efficacy assessments), [6.3.8](#) (safety assessments) and [6.5.1](#) (unscheduled visits).

## **4 SUBJECT ELIGIBILITY AND WITHDRAWAL CRITERIA**

To be eligible for this study, subjects must meet all of the inclusion criteria and none of the exclusion criteria.

### **4.1 Inclusion Criteria**

A subject must meet all of the following inclusion criteria to be eligible for participation in the study.

1. Completed the antecedent study, Study ACP-103-054 or Study ACP-103-059
2. May benefit from longer term therapy with open-label pimavanserin treatment in the judgment of the Investigator
3. Is willing and able to provide informed consent. Consent for the present study **must be** obtained prior to the procedures being performed at the Week 6/EOT visit of Study ACP-103-054 or Study ACP-103-059

4. Is capable of communicating with the site personnel, able to complete subject-reported outcome measures and can be reliably rated on assessment scales (in the opinion of the Investigator)
5. If the subject is female, she must not be pregnant or breastfeeding. She must also be of non-childbearing potential (defined as either surgically sterilized or at least 1 year postmenopausal) OR must agree to use TWO clinically acceptable methods of contraception during the study and 1 month following completion of the study.

Acceptable methods of contraception include the following:

- a. A barrier method (condom, diaphragm, or cervical cap) with spermicide
- b. Hormonal contraception, including oral, injectable, transdermal, or implantable methods
- c. Intrauterine device (IUD)

Only one of the two clinically acceptable methods can be a hormonal method.

## 4.2 Exclusion Criteria

A subject must meet none of the following exclusion criteria to be eligible for the study.

1. Is judged by the Investigator or the Medical Monitor to be inappropriate for the study, due to AEs, medical condition, or noncompliance with investigational product or study procedures in Study ACP-103-054 or Study ACP-103-059, or is judged to be a danger to self or others
2. Has any of the following electrocardiogram (ECG) results at Baseline (i.e., Week 6/ EOT visit of Study ACP-103-054 or Study ACP-103-059):
  - a. If the subject is **not** on citalopram, escitalopram, or venlafaxine (immediate or extended release):
    - i. QTcF >450 ms, if QRS duration <120 ms
    - ii. QTcF >470 ms, if QRS duration  $\geq$ 120 ms
  - b. If the subject is on citalopram, escitalopram, or venlafaxine (immediate or extended release):
    - i. QTcF >425 ms, if QRS duration <120 ms
    - ii. QTcF >450 ms, if QRS duration  $\geq$ 120 ms
3. Has a heart rate (as measured by peripheral pulse rate) <50 beats per minute at Baseline (i.e., the Week 6/EOT visit of Study ACP-103-054 or Study ACP-103-059) not explained by regular exercise or medication, in discussion with the Medical Monitor

4. Has a body mass index (BMI)  $<18.5 \text{ kg/m}^2$  or known unintentional clinically significant weight change (i.e.,  $\pm \geq 7\%$  of body weight) in Study ACP-103-054 or Study ACP-103-059 as assessed by the Investigator
5. Has clinically significant laboratory abnormalities that, in the judgment of the Investigator or Medical Monitor, would either:
  - a. jeopardize the safe participation of the subject in the study; OR
  - b. would interfere with the conduct or interpretation of safety or efficacy evaluations in the study
6. Is suicidal as defined below at Visit 1 (Baseline) of the present study:
  - a. An answer of “yes” to C-SSRS questions 4 or 5 (current or over the last 6 months); OR
  - b. Has attempted suicide within 1 year prior to Visit 1 (Baseline); OR
  - c. Is actively suicidal in the Investigator’s judgment
7. Has developed delirium or a neurologic, cardiovascular, respiratory, gastrointestinal, renal, hepatic, hematologic, or other medical or mental disorder, including cancer or malignancies that, in the judgment of the Investigator or the Medical Monitor, would increase the risk associated with taking study medication or significantly interfere with the conduct or interpretation of the study
8. Requires treatment with a medication or other substance that is prohibited by the protocol
9. Has a significant sensitivity or allergic reaction to pimavanserin or its excipients
10. Is an employee or is a family member of an employee of ACADIA Pharmaceuticals Inc.

### **4.3 Subject Withdrawal of Consent**

In accordance with the Declaration of Helsinki and other applicable regulations, a subject has the right to withdraw from the study at any time, and for any reason, without prejudice to his or her future medical care.

Should a subject request or decide to withdraw consent, every reasonable effort should be made to complete and report observations as thoroughly as possible up to the date of withdrawal, including the evaluations specified at the ET or safety follow-up visit (whichever visit is applicable), as outlined in [Table S-1](#).

### **4.4 Subject or Study Discontinuation**

Subjects may be discontinued from the study for a number of reasons, including, but not limited to, those listed below:

- Adverse event
- Death
- Lack of efficacy
- Lost to follow-up (Section 4.5)
- Non-compliance with study drug
- Physician decision
- Pregnancy
- Protocol deviation
- Study terminated by Sponsor
- Use of prohibited medication
- Other

The Sponsor reserves the right to discontinue the study at any time for any reason. Such reasons may be any of, but not limited to, the following:

- Occurrence of AEs unknown to date in respect of their nature, severity, and duration or the unexpected incidence of known AEs
- Medical, ethical or business reasons affecting the continued performance of the study

Regulatory authorities also have the right to terminate the conduct of the study in their region for any reason.

#### **4.4.1 Handling of Subject Discontinuation During the Treatment Period**

Unless the subject has withdrawn consent to be contacted for this study, every reasonable effort should be made to complete Visit 9/ET and the safety follow-up visit (as outlined in [Table S-1](#)) if a subject discontinues prematurely during the treatment period of the study for any reason. All information will be reported on the applicable pages of the electronic case report form (eCRF).

If a subject is discontinued from the study because of an AE, every reasonable attempt should be made to follow the subject until the AE resolves or until the Investigator deems the AE to be chronic or stable. For subjects who continue to be followed for safety, SAEs should continue to be reported as described in [Section 7.4.2](#). All SAEs will continue to be followed until such events have resolved or the Investigator deems them to be chronic or stable.

